4.1. Inclusion Criteria

Patients must satisfy all of the following criteria at the screening visit unless otherwise stated:

1. Willing and able to provide informed consent.
2. Male or female patients between 18 and 80 years of age.
3. Oxygen saturation <94% in room air at screening.
4. Hospitalized with mild COVID-19 disease (not requiring oxygen therapy [WHO COVID-19 Clinical Improvement Ordinal Scale, score of 3] or requiring oxygen therapy by mask or nasal prong [WHO COVID-19 Clinical Improvement Ordinal Scale, score of 4]). Requirement of oxygen therapy by mask with reservoir to treat severe COVID-19 pneumonia is not allowed for enrollment.
Note: Hospitalized patients can also include patients admitted to centers conditioned as hospitals to treat COVID-19 patients.
5. Chest x-ray or CT scan consistent with pneumonia.
6. Onset of COVID-19 symptoms within 2 weeks prior to randomization.
7. SARS-CoV-2 infection confirmed by a PCR test, antigen, or any authorized commercial or public health assay (nasopharyngeal, oropharyngeal, or respiratory samples, not serology testing).
8. Male patients and female patients of childbearing potential must agree to use protocol-specified methods of contraception ([Appendix 4](#)).
9. Female patients of childbearing potential must have a negative pregnancy test at screening or pretreatment on Day 1.
10. Male patients must agree not to donate sperm from the first dose through 90 days after the last dose of study treatment; female patients of childbearing potential should refrain from donation of ova from Day 1 until 90 days after the last dose of study treatment.
11. Patient is, in the opinion of the investigator, willing and able to comply with the study treatment regimen and all other study requirements.

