7. STUDY ASSESSMENTS AND PROCEDURES

Study procedures and their timing are summarized in the Schedule of Assessments ([Appendix 5](#)). As protocol waivers or exemptions are not allowed, with the exception of immediate safety concerns, deviations should be discussed with the sponsor immediately upon occurrence or awareness to determine if the patient should continue or discontinue the study treatment. Adherence to the study design requirements, including those specified in the Schedule of Assessments, is essential and required for study conduct.

All screening evaluations must be completed and reviewed to confirm that potential patients meet all eligibility criteria. The investigator will maintain a screening log to record details of all patients screened and to confirm eligibility or record reasons for screening failure ([Section 4.4.1](#)), as applicable. Procedures conducted as part of the patient's routine clinical management (eg, blood count) and obtained before signing the informed consent form (ICF) may be utilized for screening or baseline purposes provided the procedure met the protocol-specified criteria and was performed within the timeframe defined in the Schedule of Assessments ([Appendix 5](#)). Additionally, patients will receive instructions for home administration of study treatment and a diary to capture all doses after a discharge.

Results of the confirmatory COVID-19 test already done as SoC can be used to determine eligibility. The test does not need to be repeated at screening if already confirmed and documented. A confirmatory test may be done at screening if the COVID-19 test is not documented as SoC.

At screening, laboratory tests and ECGs will be performed locally, as applicable, to assess eligibility and do not need to be repeated if already done as SoC (eg, within 24 to 48 hours of screening and patient is clinically stable). Chest x-ray or CT scan will be performed, as applicable, to assess eligibility and does not need to be repeated if done within 48 hours of screening. In addition, baseline central laboratory test samples can be taken after confirming eligibility. Baseline laboratory samples can be obtained at screening or on Day 1 (predose). Postbaseline laboratory samples do not need to be taken predose.

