### 7.4 Baseline Disease Characteristics

Baseline disease characteristics will be listed and summarized by treatment group and overall for the ITT set. Standard descriptive statistics will be presented for the continuous variables of:

- oxygen saturation (SpO2) (%);
- WHO COVID clinical improvement ordinal scale.

The total counts and percentages of patients will be presented for the categorical variables of:

- patient setting;
- chest imaging result (normal, abnormal NCS, abnormal CS);
- SARS-CoV-2 test result (negative, positive);
- WHO COVID clinical improvement ordinal scale (at or below each score);
- COVID-19 symptoms;
- COVID-19 symptoms – maximum severity;
- patients with diarrhea.

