### 7.6 Efficacy

Efficacy analyses will be conducted on ITT set, mITT set and PPS, separately, unless otherwise specified. The ITT set will be the primary analysis population for efficacy and the mITT set and PPS will be the supportive analysis populations for efficacy analysis. If it turns out that ITT and mITT populations are identical, then only ITT results will be presented.

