#### 7.6.2 Secondary Efficacy Analysis

##### 7.6.2.1 Clinical Improvement Score as Measured by WHO COVID-19 Clinical Improvement Ordinal Scale

Clinical improvement measured as a score on the WHO COVID-19 Clinical Improvement Ordinal Scale will be analyzed using an ordinal logistic regression on Days 7, 14, and 28, with study treatment, clinical improvement score at baseline (as numerical variable), age at baseline ( $> 65$  years vs  $\leq 65$  years), and remdesivir or other authorized treatments for COVID-19 use at baseline (yes vs no) as covariates. The p-value for treatment effect will be provided based on the Wald test.

In addition, descriptive statistics will be provided for average score by treatment group, and the proportion of patients at or below each score, at each visit.

Time to 2-point improvement from baseline in WHO COVID-19 Clinical Improvement score, time to score of 2 or lower, and time to score of 0, will also be analyzed. The hazard ratio and its 95% confidence interval for these time-to-event endpoints will be estimated by Cox proportional hazard model, with treatment, remdesivir or other authorized treatments for COVID-19 use at baseline (yes vs no) and age at baseline ( $> 65$  years vs  $\leq 65$  years) as covariates. The analysis will be carried out using two different censoring rules: 1) Patients will be censored at the time they are provided any authorized treatment for COVID-19 not prescribed at baseline, or on Day 28 if they have not yet recovered or have died by Day 28; 2) Patients will only be censored on Day 28 if they have not yet recovered or have died by Day 28. The p-value for comparison between treatment groups will be obtained based on the Cox proportional hazards model described above. Median time to 2-point improvement, time to score of 2 or lower, and time to score of 0 will be estimated by Kaplan-Meier (KM) method, and the KM curve will be provided.

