### 7.6.2.3 SARS-CoV-2 PCR Test

Time to virological clearance, measured as study days from start of treatment to first negative SARS-CoV-2 PCR test, will be evaluated using similar statistical methods as clinical improvement where in this case, the first negative SARS-CoV-2 PCR test is considered as an event. Patients will be censored on Day 28 if they have not yet shown SARS-CoV-2 PCR negative or have died by Day 28.

If quantitative SARS-CoV-2 PCR results are available, the following analyses will be conducted. Note that if a patient has tested negative, they are assumed to be negative until they are tested again and for negative test result, viral load is assumed to be half of the lower limit of detection.

- Rate of change in viral load will be estimated using a Mixed Model for Repeated Measurements model.

The model will include the treatment group, age at baseline ( $> 65$  years vs  $\leq 65$  years), remdesivir or other authorized treatments for COVID-19 use at baseline (yes vs no), log (viral load) at baseline, study day (numerical, 0 for baseline), and the interaction between study day and the treatment group as fixed factors, patient as random factor (random intercept and random slope).

The model will use natural-log-transformed viral load as the response variable.

An unstructured covariance structure will be used. In case of a convergence problem with the unstructured covariance matrix, the following structures with robust sandwich estimator for the standard error of the fixed effect estimates will be assessed in a sequential fashion: heterogeneous Toeplitz, heterogeneous first-order autoregressive, Toeplitz and compound symmetry.

The estimate of the study day\*treatment will be interpreted as the difference between treatment and placebo groups in terms of the rate of change in viral load. The estimate, standard error and p-value of study day\*treatment will be reported.

- Natural-log-transformed viral load with change from baseline will be summarized by treatment group and visit using descriptive statistics.
- Arithmetic mean (+SD) of natural-log-transformed viral load vs. time figure for each treatment group will be presented.

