- a Patients will undergo assessment during hospitalization or could be discharged after start of study treatment any time after Day 2 if judged to be ready for discharge. If discharged, patients will then be requested to take study treatment at home (as prescribed) up to Day 14. End of Treatment assessments at Day 14 ( $+2$  days) (at home or site visit) will be performed. A Day 5 visit (at home or site visit) will be performed if the patient is discharged prior to Day 5. If the patient is discharged after completion of treatment and before the follow up visit, he/she will be followed up on Day 28 ( $\pm 2$  days) for study assessments (a telephone or telemedicine visit). Post discharge, assessments will be done by telephone or via telemedicine or other means of remote communication, except for Day 5, Day 14 ( $+2$  days), and Early Termination of Study Treatment, which would be a home visit.
- b Initial sentinel cohort of 20 patients to be enrolled to assess safety, tolerability, efficacy, and PK. Enrollment will pause after the 20th patient in the sentinel cohort has started treatment, until the results of the interim analysis are known. Once the 20th patient in the sentinel cohort has completed 14 days of treatment, an unblinded DMC will assess the safety, tolerability, efficacy, and PK of 100 mg BID antroquinonol in COVID-19 patients in the sentinel cohort (interim analysis 1). The DMC will issue a recommendation to enroll patients for the expansion cohort, or to stop the study depending on the safety and futility assessment. Once the 80th patient has been enrolled and completed 14 days of treatment, the DMC will review the safety, tolerability and efficacy data (interim analysis 2). Enrollment may be restricted at the 100th patient until the DMC has completed the assessment to prevent excessive enrollment.
- c Patients must satisfy all of the criteria at the screening visit unless otherwise stated (e.g. some criteria can be evaluated at Day 1 if needed).
- d Daily study treatment administration from Day 1 to Day 14.

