## Statistical Analysis Plan

Sponsor Name: Golden Biotechnology Corporation  
Sponsor Protocol ID: GH Covid-2-001

Covance Study ID: 000000203201

- h Efficacy parameter assessments: [1] Confirmation of whether the patient is discharged to home, is in the hospital, or has worsened to require an ICU. The number of days a patient has been hospitalized prior to study entry will be recorded in the eCRF. [2] PCR testing for SARS-CoV-2 will be performed by a local or central laboratory at screening. Results of confirmatory COVID-19 test already done as standard of care can be used to determine eligibility. All subsequent tests will be performed by a central laboratory at baseline/Day 1, Day 5 and Day 14. Also at Follow-up/EOS if patient is hospitalized. Either nasopharyngeal or mid-turbinate samples are allowed for central testing. Only one method should be used throughout the study for the participant. [3] Clinical improvement score will be measured using the WHO COVID-19 Clinical Improvement Ordinal Scale (refer to Appendix 7 of the protocol). [4] Patient mortality will be recorded up to Day 28. Every effort will be made to ascertain vital status in all randomized patients (e.g., with a vital records search) up to Day 28. [5] Respiratory failure is considered as patient need for invasive mechanical ventilation, non-invasive ventilation, high-flow oxygen, or ECMO. The date of the start of the respiratory intervention must be recorded in the eCRF; no daily assessment is needed. [6] COVID-19 symptoms (presence or absence of dry cough, dyspnea (shortness of breath/ difficulty in breathing), or chills/rigors, myalgia (muscle pain), headache, sore throat, and loss of taste or smell; other symptoms that could be related to COVID-19) will also be assessed during hospitalization, on discharge, ET/EOT and Follow-up/EOS visit (at the site, home visit, or via telephone or telemedicine if patient has been discharged).

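### Time to virological clearance counts patients already PCR-negative at baseline as clearing, and carries untested outpatients as uncleared to Day 28

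*SAP*

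**What the plan says.** **Event and censoring.** SAP 7.6.2.3 measures time from start of treatment to the first negative PCR, using methods similar to those for clinical improvement. Its censoring rule is "Patients will be censored on Day 28 if they have not yet shown SARS-CoV-2 PCR negative or have died by Day 28". SAP 6.2 refers time-to-event censoring to the efficacy section, and no last-test rule appears there.

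**Analysis set.** SAP 7.6 states: "Efficacy analyses will be conducted on ITT set, mITT set and PPS, separately, unless otherwise specified". Nothing in 7.6.2.3 restricts the clearance analysis by baseline PCR result.

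**PCR schedule.** Central PCR is planned at Day 1, Day 5 and Day 14. Both schedules mark PCR in the follow-up column, but footnote h in each qualifies it: "Also at Follow-up/EOS if patient is hospitalized". For discharged patients, SAP Appendix 2 footnote a says "Post discharge, assessments will be done by telephone or via telemedicine or other means of remote communication, except for Day 5, Day 14" and early termination of treatment. Their Day-28 contact is therefore remote, with no swab planned.

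**Entry.** Protocol 4.1 accepts "SARS-CoV-2 infection confirmed by a PCR test, antigen, or any authorized commercial or public health assay", with symptom onset up to two weeks before randomization. Protocol Section 7 adds, of a test already done as standard of care: "The test does not need to be repeated at screening if already confirmed and documented". SAP 7.4 tabulates the baseline test result as negative or positive.

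**Deaths.** Protocol 8.4.2 treats patients who die as not having cleared the virus by Day 28.

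**The concern.** A patient whose Day-1 central PCR is already negative cannot clear virus on treatment. Followed as written, the analysis still records that patient's first on-study negative as an event, at the same rate in both arms. This pulls a real effect toward the null and needs no imbalance between arms.

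Separately, a discharged patient still positive at Day 14 has no further planned test but stays in the risk set as uncleared to Day 28. The plan treats absence of a test as evidence of persistent virus. Protocol 3.4 describes typical stays of 5 to 7 days for patients who progress without a ventilator, so most patients would be outpatients by Day 28. The Kaplan-Meier curve after Day 14 would then largely reflect who was swabbed.

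Viral suppression is one of the goals named in Protocol 1.1, so this endpoint will be read as part of the proof of concept.

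**Working it through.** The documents give no event count, power or clearance rate for this endpoint, so there is no plan figure to reproduce. All clearance rates and baseline-negative shares below are assumptions.

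**Inputs.** 87 per arm (174 randomized 1:1, Protocol 8.1). Tests at Days 5 and 14, and at Day 28 in inpatients only (footnote h). Assumed conditional clearance q at Days 5, 14 and 28: fast 35%, 50%, 80%; slow 20%, 40%, 60%. Treated clearance is 1-(1-q)^1.5 for a true hazard ratio (HR) of 1.5; HR above 1 favours the drug. 10% are inpatients at Day 28 unless stated.

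**1. Baseline negatives.** Take 20% negative, fast rates, with their first on-study negative at Day 5.
- Placebo events at Day 5: 0.8×0.35 + 0.2 = 0.48.
- Drug events at Day 5: 0.8×(1-0.65^1.5) + 0.2 = 0.8×0.476 + 0.2 = 0.581.
- Ratio of cumulative hazards to Day 5: ln(0.419)/ln(0.52) = 1.33, where the true ratio is 1.5.

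A Cox model fitted to expected counts over all three visits gives:

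| Baseline negative | Fast, Efron / Breslow ties | Slow, Efron / Breslow ties |
|---|---|---|
| none | 1.47 / 1.32 | 1.48 / 1.37 |
| 5% | 1.44 / 1.30 | 1.44 / 1.33 |
| 10% | 1.41 / 1.28 | 1.40 / 1.30 |
| 20% | 1.36 / 1.24 | 1.34 / 1.25 |

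Simulated log-rank power with none, 10% and 20% negative (2% missed Day-14 swabs in both arms):
- One-sided 0.025: 59%, 51%, 44% (fast); 51%, 43%, 35% (slow).
- One-sided 0.2, the design threshold: about 92%, 88%, 84% (fast); 88%, 83%, 77% (slow).
- With no true effect and 20% negative, the false-trend rate stays at about 20%.

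The placebo median moves from Day 14 to Day 5 only if the negative share b satisfies b + (1-b)q ≥ 0.5 at Day 5. That means b ≥ 0.15/0.65 = 23% (fast) or 0.30/0.80 = 38% (slow).

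**2. Day-28 censoring: level of the curve.** One arm, no baseline negatives.
- Fast, true: 1 - 0.65×0.50×0.20 = 93.5% cleared by Day 28. Under the plan, with 10% tested: 1 - 0.325×(1 - 0.10×0.80) = 70.1%. Shortfall 23 points.
- Slow, true: 1 - 0.80×0.60×0.40 = 80.8%. Under the plan: 1 - 0.48×(1 - 0.10×0.60) = 54.9%. Shortfall 26 points.

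Clearance by Day 14 is 67.5% or 52%, so the median is unaffected. A separate simulation with exponential clearance times (placebo median 8 to 16 days, true HR 1.5, 5-10% inpatients) gave shortfalls of about 16 to 24 points.

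**3. Day-28 censoring: hazard ratio with no true effect.**
- Equal inpatient shares: HR 1.00.
- Inpatients 11% drug vs 22% placebo. This is a deliberately high case, in which every failure assumed in Protocol 8.1 is alive and in hospital. Per 100 fast patients in each arm, 32.5 are uncleared after Day 14. Day-28 events are 32.5×0.11×0.80 = 2.9 on drug and 32.5×0.22×0.80 = 5.7 on placebo. HR is 0.96 (fast) or 0.94 (slow), under 0.3 of a standard error and against the drug.
- Inpatients 5.5% vs 11%: 0.98 or 0.97.
- Missed Day-14 swabs, 2% in both arms: 1.00. With 1% vs 3%: 1.01, and a false promising trend in 22% of trials where 20% is nominal.

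**The case against.** **The censoring half does little to the comparison.** This is right. With equal testing the HR is 1.00, the median does not move, and the high-imbalance case is conservative for the drug. A reader might infer that the Day-28 rule biases the treatment effect materially or manufactures a positive finding. The documents do not support that: they give no reason to expect a large difference in testing between arms, and the calculated shifts are small. What stands is the distortion of the curve after Day 14, which SAP 7.6.2.1, adopted by 7.6.2.3, requires to be shown.

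**The power loss looks worse at 0.025 than at 0.2.** Also right. At the design threshold, 20% negatives cost about 8 points (fast) or 11 (slow), against 15 or 16 at 0.025.

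**Everything rests on assumed rates.** True, and with 5% negatives the effect is small. The choice of tie method moves the HR (1.47 vs 1.32) more than 10% negatives do. The direction of the dilution does not depend on the assumed values.

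**The text may already deal with baseline negatives.** SAP 5.4.1 removes from the PPS patients without confirmed infection at screening. It does not reach a patient with an earlier positive test and a negative Day-1 central PCR, and it does not touch ITT. The SAP's assumption that a negative patient stays negative until retested belongs to the viral-load analysis. Equally, neither document says outright that baseline negatives are to count as cleared; this follows because nothing removes them.

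**Day 28 is in the objective.** It is, so ending the main comparison at Day 16 would drop a named time point. That is a debatable trade-off, better handled as a sensitivity analysis.

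**The remaining wording gaps are minor.** Agreed. Whether "Patients will be censored at the time they are provided any authorized treatment for COVID-19 not prescribed at baseline" carries over from SAP 7.6.2.1 is not stated, although 7.6.2.3 gives its own censoring sentence. The phrase in Protocol 7.1.2.3 limiting PCR to the hospital stay defers to the schedule.

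**Conclusion.** The point holds for this secondary endpoint and should be corrected before unblinding. Applied as written, the rules give a diluted HR if some patients are PCR-negative at baseline: about 1.41 with 10% and 1.34-1.36 with 20%, against about 1.47 with none and a true 1.5 (Efron ties). They also understate Day-28 clearance by about 23 to 26 points with 10% inpatients; equivalently, the not-cleared curve is too high.

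These sizes rest on assumed clearance rates, baseline-negative shares and inpatient shares. The dilution cannot create a false signal. The censoring matters to the HR only if testing differs by arm. Keeping deaths as uncleared follows the protocol and is not a fault. The primary analysis and the sample size are untouched.

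**What to change.** In SAP 7.6.2.3:

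1. Make patients with a positive baseline central PCR the main set for time to clearance, with all-ITT as a sensitivity analysis. State how a missing Day-1 central result is handled.
2. Censor living patients without a negative result at their last PCR sample. Keep deaths as not cleared to Day 28, as Protocol 8.4.2 states.
3. Prespecify a comparison through the Day-14 window (Day 16) as a sensitivity analysis, and report the number PCR-tested at Day 28 in each arm. This is needed because last-PCR censoring still leaves a null HR of 0.97 to 0.98 if 5% die in each arm and inpatients are 11% vs 22%. Stopping at Day 16 gives 1.00.

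Record the change in SAP Section 8, which now declares none. As clarifications only: say whether censoring at new authorized treatment applies here, name the tie method, and align the Day-28 PCR wording with footnotes a and h.

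**Cost.** No new data, since Day-1 central PCR and sample dates are already scheduled. The main set shrinks: 174×0.8 is about 139 if 20% are baseline negative. Power does not suffer: with 20% negative, the baseline-positive set gives 51% against 44% under the plan (fast) and 43% against 35% (slow) at one-sided 0.025.

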- The hazard ratio and its 95% confidence interval for time to event outcomes will be estimated by the Cox proportional hazard model, with patients censored at the time they are provided any antiviral therapy not prescribed at baseline, or on Day 28 if they have not yet recovered. Patients who die at any time will be considered not yet recovered by Day 28. Median time to 2-point improvement, time to score of 2 or lower, and time to score of 0 will be estimated by Kaplan-Meier (KM) method, and the KM curve will be provided. The p-value for comparison between groups will be obtained based on proportional hazards modeling stratified by the same covariates as the primary model.
- Duration of hospitalization and ICU stay up to Day 28 will be analyzed using normal regression, using the same covariates as for the primary endpoint. Patients who have died will be considered as continuing to require hospitalization or ICU up to Day 28 for the purposes of this analysis.
- Time to virological clearance, measured as study days from start of treatment to first negative SARS-CoV-2 PCR test, will be evaluated using similar statistical methods as clinical improvement. All patients who have died will be considered as not having cleared the virus by Day 28.
- Rate of change in viral load will be summarized descriptively and estimated using a Mixed Model for Repeated Measurements model. The model will include the treatment group, age, remdesivir or other authorized treatments for COVID-19 use at baseline, visit, and the interaction between visit and the treatment group as fixed factors, and will include the baseline value as a covariate.
- Proportion of patients with vital status of death in both groups on Days 7, 14, and 28 will be analyzed using logistic regression stratified by the same covariates as the primary model.
- Proportion of patients alive and free of respiratory failure on Days 7 and 28 will be compared using the same analysis as the primary endpoint.
- COVID-19 symptoms at screening and on Days 7, 14, and 28 will be summarized, and compared using logistic regression following the same method as the primary endpoint.

Exploratory Analyses

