8.4.2. Secondary efficacy outcome measures

Clinical improvement measured as a score on the WHO COVID-19 Clinical Improvement Ordinal Scale will be analyzed at each timepoint, adjusted for the clinical improvement score at baseline, age at baseline, and remdesivir or other authorized treatments for COVID-19 use at baseline, using an ordinal logistic regression on Days 7, 14, and 28. In addition, descriptive statistics will be provided for average score, and the proportion of patients at or below each score, at each timepoint. Time to 2-point improvement from baseline in WHO COVID-19 Clinical Improvement score, time to score of 2 or lower, and time to score of 0, will also be analyzed.

The hazard ratio and its 95% confidence interval for time to event outcomes will be estimated by Cox proportional hazard model, with patients censored at the time they are provided any antiviral therapy not prescribed at baseline, or on Day 28 if they have not yet recovered. Patients who die at any time will be considered not yet recovered by Day 28. Median time to 2-point improvement, time to score of 2 or lower, and time to score of 0 will be estimated by Kaplan-Meier (KM) method, and the KM curve will be provided. The p-value for comparison between groups will be obtained based on proportional hazards modeling stratified by the same covariates as the primary model.

Duration of hospitalization and ICU stay up to Day 28 will be analyzed using normal regression, using the same covariates as for the primary endpoint. Patients who die will be considered as continuing to require hospitalization or ICU stay up to Day 28 for the purposes of this analysis.

Time to virological clearance, measured as study days from start of treatment to first negative SARS-CoV-2 PCR test, will be evaluated using similar statistical methods as clinical

improvement. All patients who have died will be considered as not having cleared the virus by Day 28

Rate of change in viral load will be summarized descriptively and estimated using a Mixed Model for Repeated Measurements model. The model will include the treatment group, age, remdesivir or other authorized treatments for COVID-19 use at baseline, visit, and the interaction between visit and the treatment group as fixed factors, and will include the baseline value as a covariate. If a patient has tested negative, they are assumed to be negative until they are tested again.

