### 3.2 Secondary Efficacy Endpoints

- Clinical improvement score as measured by the WHO COVID-19 Clinical Improvement Ordinal Scale, as follows:
  - Time to 2-point improvement from baseline.
  - Supportive analysis, time to score 2 or lower.
  - Supportive analysis, time to score 0.
- Duration of hospitalization (days) up to Day 28
- Virological clearance evaluated using PCR testing from nasopharyngeal or mid-turbinate samples on Day 5, 14, and 28:
  - Time to virological clearance, measured as study days from start of treatment to first negative SARS-CoV-2 PCR test
  - Rate of change in viral load will be evaluated depending on availability of quantitative assays.
- Vital status (death) on Days 7, 14, and 28
- Duration of ICU stay up to Day 28
- Proportion of patients alive and free of respiratory failure on Days 7 and 28
- COVID-19 symptoms on Days 7, 14, and 28. Assessment will evaluate: presence or absence of dry cough, dyspnea (shortness of breath/ difficulty in breathing), or chills/rigors, myalgia (muscle pain), headache, sore throat, and loss of taste or smell; other symptoms that could be related to COVID-19 will also be recorded.

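### The protocol's death rule for time to virological clearance, and the SAP's if read literally, overrides a negative PCR seen before death and so contradicts the endpoint definition

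*SAP*

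**What the plan says.** SAP 3.2 defines the endpoint as "Time to virological clearance, measured as study days from start of treatment to first negative SARS-CoV-2 PCR test". SAP 7.6.2.3 repeats this and adds that "the first negative SARS-CoV-2 PCR test is considered as an event". The analysis is by Cox model and Kaplan-Meier, since the endpoint "will be evaluated using similar statistical methods as clinical improvement".

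The death rule is stated in two places:

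- SAP 7.6.2.3: "Patients will be censored on Day 28 if they have not yet shown SARS-CoV-2 PCR negative or have died by Day 28". The two conditions are joined by 'or', so on its face death alone is enough.
- Protocol 8.4.2, and the same sentence in the synopsis: "All patients who have died will be considered as not having cleared the virus by Day 28". No exception is made for a negative test obtained before death.

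On viral load, SAP 7.6.2.3 says that "if a patient has tested negative, they are assumed to be negative until they are tested again". SAP section 8 states that the analysis methods do not differ from the protocol.

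**The concern.** The definition looks only at the swab. The death rule lets a later, non-virological outcome cancel a swab result already on file. The same Day 5 negative would then count as negative in the viral-load model and as not cleared in the Cox model.

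The study rationale (protocol 1.1) claims both antiviral and anti-inflammatory activity. Clearance and viral load are the measures that isolate the antiviral part, and viral load is analysed only if quantitative assays are available. If the drug improved survival without touching the virus, more observed clearances would be cancelled on placebo than on drug, and the hazard ratio would favour antroquinonol. If the drug worsened survival, a real antiviral effect would be partly hidden. Deaths have their own analysis on Days 7, 14 and 28, so cancelling the PCR result adds no mortality information.

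**Working it through.** **1. Three records under the literal rule.**

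| Record | By the definition | By the death rule |
|---|---|---|
| Negative Day 5, alive at Day 28 | event Day 5 | event Day 5 |
| Positive Days 5 and 14, dies Day 20 | no event | no event, held to Day 28 |
| Negative Day 5, dies Day 20 | event Day 5 | no event, held to Day 28 |

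Only the third record conflicts. It can occur. SAP Appendix 2, note h: "All subsequent tests will be performed by a central laboratory at baseline/Day 1, Day 5 and Day 14", with a further test at follow-up only if the patient is in hospital. Deaths are recorded to Day 28, so a negative can precede death by up to 28 − 5 = 23 days.

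**2. Inputs for the size.** The documents give no clearance rates, no trial-specific mortality and no power figure for this endpoint, so there is no plan figure to reproduce. From the documents: 174 patients at 1:1 (87 per arm), swabs on Days 5 and 14, thresholds of one-sided 0.2 (promising trend) and 0.025. Assumed: identical clearance in both arms (25% by Day 5, 65% by Day 14), deaths uniform over Days 2 to 28, no covariates.

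**3. Cancelled negatives.** Of the 26 days of death time, 9 lie between the two swabs and 14 after Day 14. The share of deaths with an earlier negative is (9 × 0.25 + 14 × 0.65)/26 = 11.35/26 = 0.4365. Per arm this is 87 × m × 0.4365 for mortality m:

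- m = 10%: 3.8; m = 5%: 1.9; m = 2.5%: 0.9
- m = 21%: 8.0; m = 10.5%: 4.0

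**4. Hand check of the hazard ratio.** Proportion with an event:

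- as written: F = 0.65(1 − m)
- observed negatives kept: F = 0.65 − 0.25(3m/26) − 0.40(12m/26) = 0.65 − 0.2135m

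Approximate HR = ln(1 − F drug)/ln(1 − F placebo). An HR above 1 favours the drug. At 10% vs 5%:

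- as written: ln(0.3825)/ln(0.4150) = 0.961/0.879 = 1.09
- corrected: ln(0.3607)/ln(0.3713) = 1.020/0.991 = 1.03

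At 5% vs 2.5% the same formulas give 1.004/0.961 = 1.045 and 1.035/1.020 = 1.015.

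**5. Simulation** (Cox, Efron ties, 1,500 trials per setting, true clearance HR 1):

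| Mortality, placebo vs drug | HR as written | HR corrected | Promising trend as written | Promising trend corrected |
|---|---|---|---|---|
| 10% vs 10% | 0.995 | 0.994 | near nominal | near nominal |
| 5% vs 2.5% | 1.03 | 1.005 | 24% | 21% |
| 10% vs 5% | 1.09 | 1.03 | 35% | 23% |
| 21% vs 10.5% | 1.20 | 1.05 | 52% | 30% |

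The nominal trend rate is 20%. A rate near 25% has a Monte Carlo standard error of √(0.25 × 0.75/1500) = 1.1 points. A repeat run gave 28% against 22% in the 5% row and 33% against 22% in the 10% row. One-sided 0.025 is reached in about 6% against 3% of trials at 10% vs 5%, and 14% against 5% at 21% vs 10.5%.

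**6. Other clearance assumptions.** With cumulative clearance by Days 5/14/28 of 30/70/75% or 50/90/92%, and deaths over Days 3 to 27, mortality of 10% vs 5% gives HR 1.10–1.13 as written and 1.03–1.04 corrected. Mortality of 6% vs 2% gives 1.08–1.11 and 1.03. Keeping the negative and also censoring other deaths at death gives 1.00–1.01.

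**The case against.** **The SAP sentence may be meant only for patients without an event.** SAP 6.2 introduces the censoring rules for time-to-event variables as rules for data with no event, and the sentence just before the rule makes the first negative the event. On that reading the Day 5 negative stands, and the mention of death only moves the censoring date of uncleared patients from death to Day 28. Protocol 8.4 also defers to the final SAP. This is a fair reading, so one cannot say that the SAP certainly cancels observed negatives. But the protocol sentence cannot be read this way, and SAP section 8 declares no departure from it. Two programmers could build different datasets.

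**Death as failure is a recognised composite.** Alive and cleared is a defensible estimand, and the plan treats death as failure for recovery, hospital stay and ICU stay. That stands, but it is not the endpoint that SAP 3.2 defines.

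**The 21% vs 10.5% setting invites a stronger reading than the documents support.** A reader might infer that the plan expects mortality to halve from 21%, and so that a drug without antiviral effect would show a promising trend in half of trials. The 21% comes from a general hospital series that included ventilated patients, whereas this trial excludes WHO scores 5 to 7 and life-threatening conditions. The halving (22% to 11% in protocol 8.1) is assumed for the composite of death or respiratory failure, not for death. Treat that row as an upper bound.

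**The stakes are modest.** This is one secondary endpoint in a Phase 2 study, and the viral-load model, if run, has no such rule. That is also correct.

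**Conclusion.** The concern holds as a conflict between texts that needs resolving before unblinding. The protocol rule, and the SAP rule read literally, override an observed event and contradict the endpoint definition. The distortion needs a mortality difference and deaths after a negative test. Under the assumptions above it is moderate at 10% vs 5% mortality (HR about 1.09 against 1.03) and small at 5% vs 2.5% (about two cancelled negatives on placebo and one on drug). It is absent at equal mortality.

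A reader might also infer that keeping the observed negatives removes the bias. It does not fully: patients who die without a negative stay at risk to Day 28, which is a defensible convention but leaves a residual. In the upper-bound setting this is HR 1.05, or 1.11 if dying patients clear at half the rate. Every size quoted depends on clearance and mortality rates that the documents do not supply. The primary endpoint, the futility rules and the 174-patient calculation are untouched.

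**What to change.** In SAP 7.6.2.3, replace the censoring sentence with: a patient with a negative SARS-CoV-2 PCR has the event on the date of the first negative test, whether or not the patient later dies; only patients who die without a prior negative are held as not cleared to Day 28.

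Make the same limit in protocol 8.4.2 and the synopsis, or list it as a change in SAP section 8. Report deaths before and after a first negative by arm, and add a sensitivity analysis that censors at death, to show the residual. That analysis assumes that dying patients would have cleared like the others, so it complements the main rule and should not replace it. The death rule for the WHO clinical score can stay, because there death is part of the scale.

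The cost is one sentence, one section 8 entry and one extra model run, with no new data. Patients who clear the virus and then die will count as virological events, and their deaths remain in the mortality analysis.
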